## 5F Procedures - Benefits, Incentives, and Costs

### 5F2 Incentives and Other Forms of Compensation

5F2.1 \* Will the participants receive incentives or some other form of compensation (e.g., cash, voucher, meals, reimbursements)?  
yes

5F2.2 \* If "Yes", what will the participants receive as an incentive or other forms of compensation?  
Participants will receive \$20 per visit to download adherence data and update their contact information

5F2.3 \* If "Yes", how and when will the incentives or other forms of compensation be distributed to participants? Include any detail about conditions under which they might not receive the incentive or other form of compensation.  
All participants who visit APLA for a study visit to download adherence data will receive \$20

### 5F3 Costs

5F3.1 \* Might the participants incur any financial costs that will not be reimbursed and that they would otherwise not incur?  
no

## 5G Procedures - Confidentiality

### 5G1 Sensitive Information

5G1.1 \* Will any of the following types of sensitive information be intentionally accessed, acquired, or recorded as part of data collection about an individual? (Check all that apply) Note: You may have answered this question 2H with regard to a specific population if you applied for an exemption for one or more population-procedure components of your study. However, we are asking this question again because the information may be sensitive with regard to another population in your study that you have associated with this procedure.

 A. Substance use	including alcohol, drugs, and tobacco
 B. Physical health	including diagnosis, treatment, or any other private physical health information
 C. Mental health	including diagnosis, treatment, current mental health status (e.g., suicidality), or any other private mental health information
 D. Traumatic events	including victimization, bereavement, accidents, natural disasters, and military combat
 E. Illegal activity	including illicit drug use, human trafficking, and terrorism
 F. Immigration status	
 G. Sexual behavior	
 H. Abuse/neglect	including child, elder, domestic, and partner
 I. Educational records	including status, history, or performance
 J. Employment records	including status, history, or performance
 K. Financial information	
 L. Other	
 M. None of the above	

ID: 2016-0940

**5G2 Identifying Information**

**5G2.1** \* Check all types of identifying information that your research will acquire about these participants. Note: You may have answered this question on screens 2B or 2C with regard to a specific population if you applied for an exemption for one or more population-procedure components of your study. However, we are asking this question again because the information may be identifiable with regard to another population in your study that you have associated with this procedure.

 A. Names	including names appearing on consent forms, payment receipts, medical records, and emergency contact lists
 B. Location and contacting information	including any address information smaller than state, telephone or fax numbers, email addresses, web URLs, and IP addresses
 C. Dates	including birth date, marriage date, and treatment or visit dates from medical records
 D. Identification numbers	including Social Security Numbers, medical record or health plan beneficiary numbers, account identification numbers, student ID numbers, certificate or license numbers (e.g., driver's license), vehicle identifiers and serial numbers (e.g., license plates), and device identifiers and serial numbers (e.g., serial numbers on surgical implants)
 E. Audio, video, or biometric indicators	including photographic or video images, audio recordings, and finger or voice prints
 F. None of the above	by checking this box you certify that you are not obtaining any of the information listed above
 F. identifiers	by checking this box you certify that you are not obtaining any of the information listed above

**5G3 Disclosure of Identifiable Person Level Data**

**5G3.1** \* Will any information that you collect go into person level non-research records (e.g., medical, educational, employment records) that are not maintained and controlled solely by the research team? Note: This is a relatively rare occurrence for research done at RAND and would require HSPC approval.

Yes

No

Don't know

**5G4 Reasons for Breaking Confidentiality**

**5G4.1** \* Could the procedure yield information potentially of importance to individual participants that they otherwise would be unlikely to know? This includes information specifically gathered or spontaneously provided or observed.  
yes

**5G4.2** \* If "Yes", will participants or others (e.g., doctors, teachers, parents) be notified?  
yes

**5G4.3** Note: If "Yes", this information must be included in the consent form.

**5G4.4** \* If "Yes", please provide a detailed explanation of who will be notified, what information will be provided (e.g., abnormal test results, reportable diseases), and how.  
At the end of their participation in the study, all participants will be presented with their electronically monitored adherence data and will go over it with the study research assistant.

**5G5 Promise of Confidentiality**

**5G5.1** \* Is confidentiality being promised to participants with no additional exceptions aside from those noted in 5G4?

A. Yes

B. No, participants can choose to allow potentially identifiable information (e.g., quotes, performance information) to be included in published reports

C. No, participants must agree to be attributable in published reports (this is a rare exception and might only occur in studies of a single organization)

D. No, there will be other exceptions (e.g., intent to harm self or others, suspected child abuse)

**5G5.4** \* If "D" on 5G5.1, please describe the exceptions and why they are necessary.

There will be legal exceptions of suicidal ideation or harm to self or others and intent to harm others or child or elder

ID: 2016-0940

abuse/neglect.

**5G5.5** \* Do you plan to apply for a Certificate of Confidentiality? Please note that such applications can be filed only after consent protocols have been approved.

 Yes No Don't know

## 5G6 Identifiability by Inference in Published Reports

---

**5G6.1** \* Might comments or other information included in published reports be identifiable by inference for participants who do not agree to be identified and are being assured of confidentiality?

no

## 5G7 Data Safeguarding Plan

---

**5G7.1** \* Based on previous answers, a Data Safeguarding Plan (DSP) is required. Are you ready to upload it in draft or final form at this time?

yes

**5G7.2** You will be able to upload the Data Safeguarding Plan (DSP) later in Section 7

---

## Intervention

### 3C Research Overview - Procedures

---

Related Populations:

- *People Living with HIV (Full Committee - Approved)*

### 3C1 Procedure Description

---

**3C1.1** \* Which of the following describes this procedure? (Check all that apply)

A. Acquiring previously collected person-level

information

(e.g., medical records, census data, employment records, education records, other existing datasets)

B. Interview

(e.g., phone interview)

ID: 2016-0940

 C. Survey (either oral or written)	(e.g., mail survey, web survey)
 D. Group discussion	(e.g., focus group, expert panel)
 E. Observation of individuals or groups	(e.g., in-person visual observation, video observation)
 F. Educational testing	(e.g., aptitude testing, military/vocational training assessment)
 G. Psychological testing, measurement, or assessment	
 H. Physical exam, testing, measurement, assessment (w/o specimen collection)	(e.g., blood pressure, weight measurement,)
 I. Biologic sample collection	(e.g., tissue, blood, urine, saliva)
 J. Testing of existing biological samples	(e.g., testing for the presence of disease or drugs)
 K. Socio-behavioral or educational intervention	(e.g., randomized trials, quasi-experimental designs, demonstration projects)
 L. Clinical treatment	(e.g., administering drugs, therapy)
 M. Other intervention research procedures	(e.g., physical procedures, manipulating environment to evaluate impact on outcome)
 N. Other interaction research procedures	(e.g., obtaining information from individuals)

**3C3** You will be asked to complete the following screens in section 5 for this procedure based on your answers given above:

- 5A Procedures - Interventions: Overview
- 5E Procedures - Risks
- 5F Procedures - Benefits, Incentives, Costs
- 5G Procedures - Confidentiality

## 5A - Procedures - Interventions: Overview

**5A1** \* Provide a step-by-step description of this procedure for the studied groups of participants. Include both alterations of their experiences (e.g., novel educational practices, new health services) and administration of any treatments they might not otherwise receive (e.g., medications, nutritional supplements). Note: you will be asked below in 5A2 about assignment of participants to different groups (e.g., different data collection or treatment/control groups). Rise consists of a one-month intensive intervention (with three core 60-minute counseling sessions at weeks 1, 2, and 4) followed by two booster sessions (at weeks 12 and 20). If participants show treatment nonadherence during booster sessions, they are offered up to four additional booster sessions (i.e., extra booster sessions if <85% of prescribed doses were taken in the past month). Thus, participants receive three core sessions in the first month, followed by 2-6 booster sessions over the next four months.

One-Month Intensive Intervention Period. Session 1: In the first session, the counselor provides information about the importance of adherence and consequences of missed doses and appointments, provides education about viral load and drug resistance, and explains the connection between dosing schedules and viral suppression. To address culturally relevant factors, the counselor acknowledges health care discrimination and health disparities, and shares reasons for medical mistrust and HIV misconceptions in Black communities. The counselor encourages the client to share any experiences and perceptions they may have in this regard. To enhance instrumental (e.g., finding transportation to clinic) and emotional (e.g., encouraging/reinforcing adherence) support, the counselor assesses the availability of social supports to the client (e.g., whether individuals in clients' social networks are aware of their HIV status). The counselor explores with the client whether HIV disclosure is an option for obtaining social support, in the context of reviewing possible benefits as well as risks. The counselor supplies accurate information to dispel any HIV-related misconceptions.

Adherence Feedback/Review: Together with the client, the counselor reviews adherence and attendance at scheduled medical appointments to provide a baseline of adherence levels that will be revisited in future sessions. Adherence will be measured electronically and continuously using MEMS caps, which record times when the medication bottle is opened. (See Assessment section for a full description.) MEMS software yields daily medication-taking reports and calculates percentage of scheduled doses taken. Intervention counselors download MEMS data and generate and print out adherence summary statistics and graphic depictions of patterns of doses taken and missed since baseline in Session 1 or since the last session in later sessions.

After the counselor identifies instances of nonadherence using MEMS data, clients identify barriers that may contribute to missed appointments and doses, such as lack of accurate treatment information (or belief in misconceptions), low motivation, presence of or concern about side effects, mental health issues or substance use, internalized stigma, medical mistrust and/or negative experiences with health care (e.g., discrimination). Stages of problem solving are reviewed: defining the problem, deciding on a goal, generating possible solutions, selecting a potential solution, planning the solution's implementation, and evaluating the solution's effectiveness (at the subsequent session). The counselor identifies contextual cues that influence adherence (what occurred immediately before and after a missed dose/appointment) to derive strategies for managing and controlling cues. Clients describe daily routines and together with the counselor determine optimal ways to

ID: 2016-0940

integrate medication into routines. Doses are connected with routine daily activities that can serve as reminder triggers for taking medications. Strategies for coping with and reducing side effects are discussed.

The counselor conducts a needs assessment and provides referrals for any unmet basic needs (housing, food, transportation) and mental health issues (depression, substance use), using pre-screeners for mental health and substance use (PHQ-2 for depression; NIDA Quick Screen for substance use). Session 1 closes with the development of an Individual Service Plan (ISP) of short- and long-term goals (e.g., following up on referrals, engaging a friend to support adherence), which is revisited and updated in each session.

Sessions 2-3: These sessions are similar to Session 1, but with greater targeting of barriers to adherence and retention in care. Together with the client, the counselor reviews adherence and attendance at scheduled medical appointments since the last session, and discusses barriers and reasons for missed doses. The counselor assesses whether clients followed up on referrals, offers new referrals as needed, and evaluates progress toward ISP goals. The counselor assesses the client's relationship with his/her HIV care provider in terms of satisfaction with care and trust in provider. With consent from the client, the counselor contacts the provider via phone or email to inform him/her that the client is participating in Rise and working with the counselor over the next 6 months to support the adherence and care retention. The client and counselor agree on any adherence barriers that the counselor can convey to the provider (e.g., about housing status).

Booster Sessions. Booster Sessions 4 & 5: The goal of the booster sessions is to help clients sustain optimal adherence. Clients who achieve ≥85% adherence (as measured by MEMS) during the 2 weeks preceding Weeks 12 and 20 receive a session only at those weeks; others receive up to two biweekly added sessions at each time point. For example, if adherence from Weeks 10-12 is ≥85%, the client receives a session at Week 12, and then returns again at Week 20 for the next booster session. If the client's adherence from Weeks 10-12 is <85%, the client receives booster sessions at Weeks 12 and 14, and if adherence from Weeks 12-14 is <85%, then s/he receives another session at Week 16. All clients return at Week 20, but only clients with adherence <85% during Weeks 18-20 return at Week 22, and those with adherence <85% during Weeks 20-22 have another session at Week 24. We use 85% adherence as the cutoff for determining good adherence based on research suggesting that this level of adherence is associated with optimal treatment response and viral suppression. The dose regulation (of 0-4 extra booster sessions) is intended to promote efficient use of limited community resources by varying intensity depending on client need. Booster sessions are similar to the initial core sessions, with continued emphasis on identification and resolution of barriers, use of MI to improve attitudes and motivation related to adherence, side effect management, monitoring of adherence-related social support and self-efficacy, and medical mistrust.

Intervention sessions take place at several APLA Health locations. If a client is unable to attend a session at APLA Health, the intervention counselor can travel to meet the participant in his/her home or a confidential location. In such instances, the counselor would find a confidential, private space in which the session cannot be overheard by others, in which others are not in earshot (e.g., in fast food restaurants, coffee shops, parks, people's homes), and would stop the session if other people enter the space and are able to overhear anything, consistent with SRG protocols for field interviewing.

In addition, due to the COVID-19 situation, APLA Health staff have been told to work at home. Thus, the intervention counselor will conduct intervention sessions by phone from home, using a dedicated study cell phone, and in a private space in which others cannot overhear (the counselor lives alone). We will modify the sessions to be done without the electronic adherence monitoring component, as that requires an in-person interaction.

## 5A2 Administered to All Members

### 5A2.1 \* Will any subgroups of the population(s) referenced above receive different interventions? (Check all that apply)

A. Yes - not all participants will receive the same intervention (e.g., physical exams or biologic samples will be collected/tested from only a subset)

B. Yes - some participants will receive the socio-behavioral or clinical intervention and others will be in the control group

C. No - all participants will receive the same procedure(s) listed above

### 5A2.4 \* If "B", please describe how individuals will be selected into the intervention/treatment and control groups (e.g., random assignment of individuals/groups or quasi-experimental designs comparing existing groups). If already described above in 5A1, please indicate that below.

A blocked 1:1 randomization design with stratification by viral suppression (with randomly alternating blocks of 2, 4, and 6 to prevent anticipation of condition) will help to ensure balance across arms. The statistician will use a random numbers generator to devise a randomization log and a set of numbered randomization envelopes. In the log, treatment assignment specifications will be left blank to prevent condition foreknowledge. After the project director records each ID in the log (immediately after the baseline survey, using results from pre-baseline confirmation of viral load via medical records for stratification), s/he will open the corresponding randomization envelope.

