**5C1.3** **\* Will the research team be audio or video recording the interaction procedure?**  
 no

**5C2** **\* Provide a step-by-step description of this procedure.** *Note: Details regarding whether the interaction procedure will be repeated are covered in 5C4.*  
 At the pre-enrollment visit, and at 6-and 12-month post-intervention start (7 and 13 months after the first study visit), participants will complete surveys using the Questionnaire Development System for audio computer-assisted self-interviews. Surveys will be completed in a private space on a computer at APLA project offices, and a study interviewer will be available to answer questions or administer the survey as needed for those of lower literacy.

Interviews may also be conducted by phone on a dedicated study cellphone, from a private location (interviewers' homes) in which the interviewer cannot be heard by others. This last option has been added because APLA Health staff have been told to work at home during the COVID-19 situation. In this case, interviewers will upload all study data (from QDS, the ACASI program) from their study laptop onto the secure Kiteworks data sharing site; study staff at RAND will download the data as soon as it is received and tell APLA staff, so that it can be deleted from the study laptop. In addition, consent for the baseline interview would be done by phone (verbally) for baseline phone interviews, and then written informed consent will be obtained when the client next is seen in person (after the COVID-19 situation is resolved).

In some cases, we may also conduct study visits off-site, if a participant is screened as eligible and unable or unwilling to travel to the study locations. We would find a confidential, private space in which the interview cannot be overheard by others, in which others are not in earshot (e.g., in fast food restaurants, coffee shops, parks, people's homes), and would stop the interview if other people enter the space and are able to overhear the interview; the team will be trained on SRG's protocols for field interviewing.

Interviewers will also interact with participants by phone, mail, and over the internet to set up appointments and to remind participants about appointments. Interviewers will also use text to remind participants about appointments. Specifically, we

ID: 2016-0940

will text reminders to participants using the dedicated study cell phone. Only the Project Rise staff team would have access to the cell phone.

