## 5F2 Incentives and Other Forms of Compensation

---

5F2.1 \* Will the participants receive incentives or some other form of compensation (e.g., cash, voucher, meals, reimbursements)?

yes

\* If "Yes", what will the participants receive as an incentive or other forms of compensation?

Assessments: Participants will receive \$30 for the baseline survey (i.e., pre-enrollment, which will also include screening, consent, and starting on MEMS), and \$40 at 6-months, and \$50 at 12-months for the follow-ups (which will also include venipuncture for viral load assessment and downloading of MEMS data).

Incentivized Recruitment: We will also offer incentives for participants in the study to recruit others in their social networks. All participants who have registered for Project Rise will be able to receive recruitment incentives, including those who are already participating in the program. Participants will be given study palm cards and materials to distribute to communities and individuals they know. When interested clients call to screen, they will be asked how they heard about the program. If the interested client provides the name of a specific individual, study staff will make a note in the electronic participant database. Study staff will notify the participant that someone they referred to Project Rise screened for the study, but they will not be provided the specific name of who it was. For each person screened (up to 3 people) and referred, the referring participant will receive \$10, for a maximum of \$30. To ensure confidentiality, participants will not be told the names of the specific clients who screened. Screening history and participation data will not be shared outside of the study team. All electronic screening information is kept in a secure spreadsheet in a folder only accessible to study team staff, and on password-protected computers and accounts. Paper screeners are kept in locked drawers at APLA Health's office in Baldwin Hills, and not shared with people outside the study team.

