**6A3 Informed Consent Material Upload**

**6A3.1** \* Do you have informed consent material(s) to upload now?

A. Yes - ready to upload now

**6A3.2** \* Do you have variations (e.g., for students at different schools) of the informed consent material?

A. Yes - the variations are minor

**6A3.4** \* Please upload the informed consent material (e.g., consent form to be signed or script for oral consent). Note: If you have variations that are substantive, refer to 6A3.3 before uploading.  
[Project Rise Consent Form edited 2020-01-17tc.docx\(0.02\)](Project Rise Consent Form edited 2020-01-17tc.docx(0.02))

**6A3.7** \* Please explain the variations. If you are uploading multiple variations in 6A3.6, please include references to the specific documents in explaining the variations.

The Consent form attached will be used for different procedures or components of this study; while the HIPPA form will be used to authorize the release of medical information by the participant. The HIPPA form has been uploaded under additional materials.

ID: 2016-0940

Note that the consent form was revised on 10/16/17 to reflect changes suggested by the reviewer as well as community stakeholder (to simplify the text), and new timing of study procedures (i.e., baseline survey will be given 1 month earlier).

Note that the consent form was again revised on 3/29/19 to reflect additions to the procedures regarding texting participants appointment reminders.

Note that the consent form was revised on Jan 17, 2020 to reflect an additional incentive of \$30 for participants obtaining medical record data directly from their provider.

Note that we are requested verbal informed consent during the COVID-19 situation, when all assessments will be done by phone. We will ask them to sign the consent form at a later date, when we are able to have in person assessments again. (Please see above explanation.)

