## 7A1 Participant Questions

ID: 2016-0940

**7A1b** \* Which of the following population-procedure study components does this document apply to? (Check all that apply)

Population	Procedure	This document applies to this population-procedure component
People Living with HIV		

**7A2a** \*\* Please upload the document.

[Pre-enrollment and baseline 10-09-2017.docx\(0.01\)](#) | [History](#)

**7A3a** Please enter any comments that you wish to share with the reviewer regarding this document.

This document combines what was previously the pre-enrollment and baseline survey questions. No questions have been changed. The documents have been combined because all questions will now be asked at the first study visit, rather than splitting the survey across the first 2 study visits. This will decrease participant burden in the second study visit (which will also include MEMS downloading, blood draws, and a possible first intervention session).

---

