## 7A6 Miscellaneous Documents

**7AX.1b** \* Which of the following population-procedure study components does this document apply to? (Check all that apply)

Population	Procedure	This document applies to this population-procedure component
People Living with HIV		

**7AX.2a** \*\* Please upload the document.

[CheckinvisitsandRandomizationform10-16-17.docx\(0.01\)](#) | [History](#)

**7AX.3a** Please enter any comments that you wish to share with the reviewer regarding this document.

Document for checking in with participants about updating contact information, downloading electronic adherence data, and randomizing (1-month session only)

Replaces check-in and use of MEMS form combined (which was similar but did not include the randomization for the first check-in)

---

---

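### Protocol 5A2.4 randomises right after a baseline survey that now falls a month before the baseline MEMS download and blood draw, contradicting the sections that randomise at the 1-month visit

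*Protocol*

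**What the plan says.** **When the envelope is opened.** Protocol 5A2.4 (Intervention) has the project director enter each ID in the log "immediately after the baseline survey, using results from pre-baseline confirmation of viral load via medical records for stratification" and then open the matching envelope. No other section describes the log, the strata and the envelopes.

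**When the baseline survey takes place.** Section 6A3.7 records a consent revision of 10/16/17 for "new timing of study procedures (i.e., baseline survey will be given 1 month earlier"). The comment in 7A1 on the combined questionnaire says that "all questions will now be asked at the first study visit, rather than splitting the survey across the first 2 study visits". Section 5F2.2 (Surveys) describes the "baseline survey (i.e., pre-enrollment, which will also include screening, consent, and starting on MEMS"), so no MEMS data exist at that point.

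**When the baseline outcomes are measured.** The same 7A1 comment refers to the "second study visit (which will also include MEMS downloading, blood draws, and a possible first intervention session"). Section 5A1 (Viral Load Assessment) also places the first study blood draw at enrollment.

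**Where else randomisation is placed.** Section 5C2 (MEMS) treats enrollment and randomisation as one visit, preceded by a month of MEMS. The 7A6 comment on the check-in form lists "downloading electronic adherence data, and randomizing (1-month session only").

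**How the values are used.** The SAP fits a repeated-measures logistic model to dichotomised MEMS adherence at enrollment and each follow-up, with a linear time trend. It models viral suppression at 6 and 12 months post-enrollment.

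**The concern.** The section that staff would consult for allocation ties it to an event that has since been moved, and the text was not changed to match. Read with the current survey timing, it assigns the arm before the MEMS run-in rather than after it.

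Three things would follow:

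- The enrollment adherence value would no longer be a pre-allocation measurement. In a repeated-measures model with a time trend, an arm difference that arises during the run-in enters at the first time point and distorts the estimated change.
- At each download, interviewers correct the last two weeks of MEMS data using participants' reports of cap use. That correction of the baseline value would be made after allocation, and the protocol describes no blinding of participants or interviewers.
- People who do not return for the second visit would count as randomised but have no baseline MEMS value and no study viral load. Their number could differ by arm.

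**Working it through.** This is a question of the order of events. The plan gives no figure to reproduce beyond its own visit timing.

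**Step 1: the gap between the two visits.** Section 5C2 (Surveys) schedules follow-up "at 6-and 12-month post-intervention start (7 and 13 months after the first study visit"). The gap is 7 − 6 = 1 month and 13 − 12 = 1 month. The intervention therefore starts one month after the first visit, which agrees with the one-month shift in 6A3.7.

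**Step 2: the two timelines side by side.**

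| Time | 5A2.4 read with the current survey timing | 5C2 (MEMS) and 7A6 |
|---|---|---|
| Month 0, first visit | Consent, survey, MEMS started, envelope opened | Consent, survey, MEMS started |
| Months 0 to 1 | MEMS run-in with the arm already assigned | MEMS run-in with no arm assigned |
| Month 1, second visit | MEMS download, first blood draw, perhaps Session 1 | MEMS download, first blood draw, envelope opened, perhaps Session 1; full order not stated |

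**Step 3: which measurements change status under the literal 5A2.4 rule.**

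- After allocation: the one-month MEMS baseline and the first study viral load.
- Still before allocation: the survey-based secondary outcomes and mediators, self-reported adherence (5C5.2, Surveys), and the medical-record viral load used for stratification (5A2.4; 5D1, Medical Records).

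**Step 4: people randomised without the affected values.** The documents give no loss rate between the first and second visits. With an assumed 5% to 20% of the planned 350:

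- 350 × 0.05 = 17.5, about 18 people
- 350 × 0.20 = 70 people

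Under 5C2 (MEMS) and 7A6 the number is zero for non-attendance, because those who do not return are never randomised.

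**Step 5: which text is out of date.** Section 3C1.5 (MEMS) still starts monitoring a month before the baseline survey. That was the sequence before the survey moved, when survey and enrollment fell together. In that sequence 5A2.4 is coherent. This points to 5A2.4 and 3C1.5 as remnants, and to 5C2 (MEMS) and 7A6 as the updated text.

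**The case against.** The best defence is that nobody was ever meant to be randomised at the first visit. The check-in form that carries randomisation has 10-16-17 in its file name, the same date as the consent revision for the survey move. The 7A6 comment says that the form it replaced had no randomisation step. So the change that moved the survey also put randomisation on the later visit's form. On this view 5A2.4 holds one stale phrase, and practice was sound. That is the likelier reading, and it stands. It does not remove the contradiction, because 5A2.4 is the section that defines the allocation procedure.

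A reader might be tempted by four stronger conclusions that the documents do not support:

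- **That every baseline outcome would be post-randomisation.** Survey measures and the stratification viral load precede the envelope even under the literal rule, so non-returners would still have some baseline data.
- **That the SAP uses the enrollment viral load as a repeated measure.** It names enrollment data only for electronic adherence; viral suppression is modelled at 6 and 12 months.
- **That counseling would contaminate the baseline.** The intervention starts at about month 1, so the affected values would be largely pre-intervention. The remaining risks are knowledge of the arm and differential dropout. Even knowledge of the arm is an inference, since 5A2.4 does not say when participants are told.
- **That the bias can be given in standard deviations.** Multiplying an assumed shift by an assumed correlation describes covariate adjustment for a continuous baseline. The SAP states no such adjustment for adherence, and its main adherence model is logistic.

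**Conclusion.** The protocol contradicts itself on when randomisation happens. Taken literally, 5A2.4 puts baseline electronic adherence and the baseline study viral load about one month after allocation; 5C2 (MEMS) and 7A6 randomise at the 1-month visit.

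The displacement of one month follows from the protocol's own visit schedule. The 18 to 70 people randomised without those values rest entirely on the assumed 5% to 20% loss and are illustrative. No bias in the treatment effect can be computed from the documents, and they do not show that anyone was randomised early.

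The point should be corrected because a literal reading would give a worse trial and the correction is almost free. Even 5C2 (MEMS) and 7A6 leave one gap: neither says whether the blood draw comes before the envelope, and 7A1 allows the first counseling session at that same visit.

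**What to change.** 1. In 5A2.4, replace the reference to the baseline survey with: *at the 1-month enrollment visit, after the baseline MEMS download and blood draw and before any counseling session*. Add that only people who attend this visit are randomised. Since 5F2.3 (Surveys) allows a participant to complete the enrollment download but decline venipuncture, say that a declined draw is recorded before the envelope is opened.
2. Align 3C1.5 (MEMS) with 5C2 (MEMS), so that monitoring is timed from the enrollment and randomisation visit rather than from the survey.
3. Accrual appears to be over or nearly so: 6A2 mentions only 3 to 5 baseline appointments outstanding during COVID-19, and 3A2.1 anticipates the end of data acquisition on 10/31/2021. If it is complete, still correct the text. Then compare each participant's randomisation date with the first MEMS download and blood-draw dates before using enrollment values as baseline. Report by arm any participant allocated earlier, and do not label that person's enrollment values as baseline.

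The cost is a sentence or two in each of two sections and one check of dates. No visits or staff are added, because the check-in form already randomises at the 1-month session.
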